2. DEFINITIONS

Potential Hy's Law (PHL)

Aspartate Aminotransferase (AST) or Alanine Aminotransferase (ALT) $\geq 3x$ Upper Limit of Normal (ULN) **and** Total Bilirubin (TBL) $\geq 2x$ ULN at any point during the study irrespective of an increase in Alkaline Phosphatase (ALP). The elevations do not have to occur at the same time or within a specified time frame.

Hy's Law (HL)

AST or ALT $\geq 3x$ ULN **and** TBL $\geq 2x$ ULN, where no other reason, other than the IMP, can be found to explain the combination of increases, eg, elevated ALP indicating cholestasis, viral hepatitis, another drug. The elevations do not have to occur at the same time or within a specified time frame.

3. IDENTIFICATION OF POTENTIAL HY'S LAW CASES

In order to identify cases of PHL it is important to perform a comprehensive review of laboratory data for any patient who meets any of the following identification criteria in isolation or in combination:

- ALT $\geq 3x$ ULN
- AST $\geq 3x$ ULN
- TBL $\geq 2x$ ULN

The Investigator will without delay review each new laboratory report and if the identification criteria are met will:

- Determine whether the patient meets PHL criteria (see Section 2 of this Appendix for definition) by reviewing laboratory reports from all previous visits
- Promptly enter the laboratory data into the laboratory CRF

4. FOLLOW-UP

4.1 Potential Hy's Law Criteria not met

If the patient does not meet PHL criteria the Investigator will:

- Perform follow-up on subsequent laboratory results according to the guidance provided in the Clinical Study Protocol.

4.2 Potential Hy's Law Criteria met

If the patient does meet PHL criteria the Investigator will:

- Notify the AstraZeneca representative who will then inform the central Study Team

The Study Physician contacts the Investigator, to provide guidance, discuss and agree an approach for the study patients' follow-up and the continuous review of data. Subsequent to this contact the Investigator will:

- Monitor the patient until liver biochemistry parameters and appropriate clinical symptoms and signs return to normal or baseline levels, or as long as medically indicated
- Investigate the etiology of the event and perform diagnostic investigations as discussed with the Study Physician
- Complete the three Liver CRF Modules as information becomes available
- If at any time (in consultation with the Study Physician) the PHL case meets serious criteria, report it as an SAE using standard reporting procedures

5. REVIEW AND ASSESSMENT OF POTENTIAL HY'S LAW CASES

The instructions in this Section should be followed for all cases where PHL criteria are met.

No later than 3 weeks after the biochemistry abnormality was initially detected, the Study Physician contacts the Investigator in order to review available data and agree on whether there is an alternative explanation for meeting PHL criteria other than DILI caused by the IMP. The AstraZeneca Medical Science Director and Global Safety Physician will also be involved in this review together with other subject matter experts as appropriate.

According to the outcome of the review and assessment, the Investigator will follow the instructions below.

If there **is** an agreed alternative explanation for the ALT or AST and TBL elevations, a determination of whether the alternative explanation is an AE will be made and subsequently whether the AE meets the criteria for a SAE:

- If the alternative explanation is **not** an AE, record the alternative explanation on the appropriate CRF
- If the alternative explanation is an AE/SAE, record the AE /SAE in the CRF accordingly and follow the AZ standard processes

If it is agreed that there is **no** explanation that would explain the ALT or AST and TBL elevations other than the IMP:

- Report an SAE (report term ‘Hy’s Law’) according to AstraZeneca standard processes.
 - The ‘Medically Important’ serious criterion should be used if no other serious criteria apply
 - As there is no alternative explanation for the HL case, a causality assessment of ‘related’ should be assigned.

If, there is an unavoidable delay, of over 3 weeks, in obtaining the information necessary to assess whether or not the case meets the criteria for HL, then it is assumed that there is no alternative explanation until such time as an informed decision can be made:

- Report an SAE (report term ‘Potential Hy’s Law’) applying serious criteria and causality assessment as per above
- Continue follow-up and review according to agreed plan. Once the necessary supplementary information is obtained, repeat the review and assessment to determine whether HL criteria are met. Update the SAE report according to the outcome of the review

6. ACTIONS REQUIRED WHEN POTENTIAL HY'S LAW CRITERIA ARE MET BEFORE AND AFTER STARTING STUDY TREATMENT (NOT APPLICABLE)

7. ACTIONS REQUIRED FOR REPEAT EPISODES OF POTENTIAL HY'S LAW

This section is applicable when a patient meets PHL criteria on study treatment and has already met PHL criteria at a previous on study treatment visit.

The requirement to conduct follow-up, review and assessment of a repeat occurrence(s) of PHL is based on the nature of the alternative cause identified for the previous occurrence.

The investigator should determine the cause for the previous occurrence of PHL criteria being met and answer the following question:

- Was the alternative cause for the previous occurrence of PHL criteria being met chronic or progressing malignant disease?

If No: follow the process described in Section 4.2 of this Appendix

If Yes:

Determine if there has been a significant change in the patient's condition[#] compared with when PHL criteria were previously met

- If there is no significant change no action is required
- If there is a significant change follow the process described in Section 4.2 of this Appendix

[#] A 'significant' change in the patient's condition refers to a clinically relevant change in any of the individual liver biochemistry parameters (ALT, AST or total bilirubin) in isolation or in combination, or a clinically relevant change in associated symptoms. The determination of whether there has been a significant change will be at the discretion of the Investigator, this may be in consultation with the Study Physician if there is any uncertainty.

Appendix F
Acceptable Birth Control Methods

1. ACCEPTABLE BIRTH CONTROL METHODS

Olaparib is regarded as a compound with medium/high foetal risk.

Women of childbearing potential and their partners, who are sexually active, must agree to the use of TWO highly effective forms of contraception in combination [as listed below], throughout the period of taking study treatment and for at least 1 month after last dose of study drug(s), or they must totally/truly abstain from any form of sexual intercourse (see below).

<include if recruiting male patients> Male patients and their partners, who are sexually active and of childbearing potential, must agree to the use of TWO highly effective forms of contraception in combination [as listed below], throughout the period of taking study treatment and for 3 months after last dose of study drug(s) due to the unknown effects of the study drug on the sperm, or they must totally/truly abstain from any form of sexual intercourse (see below). Male patients should not donate sperm throughout the period of taking study treatment and for 3 months following the last dose of study drug(s).

Acceptable Non-hormonal birth control methods include:

- Total sexual abstinence. Abstinence must continue for the total duration of study treatment and for at least 1 month after the last dose. *<<for 3 months after last dose for male patients>>*. Periodic abstinence (eg, calendar ovulation, symptothermal post ovulation methods) and withdrawal are not acceptable methods of contraception.
- Vasectomised sexual partner PLUS male condom. With participant assurance that partner received post-vasectomy confirmation of azoospermia.
- Tubal occlusion PLUS male condom
- IUD PLUS male condom. Provided coils are copper-banded

Acceptable hormonal methods:

- Normal and low dose combined oral pills PLUS male condom
- Cerazette (desogestrel) PLUS male condom. Cerazette is currently the only highly efficacious progesterone based pill.
- Hormonal shot or injection (eg., Depo-Provera) PLUS male condom
- Etonogestrel implants (e.g., Implanon, Norplant) PLUS male condom
- Norelgestromin / EE transdermal system PLUS male condom
- Intrauterine system [IUS] device (eg., levonorgestrel releasing IUS -Mirena®) PLUS male condom
- Intravaginal device (e.g., EE and etonogestrel) PLUS male condom

Clinical Study Protocol Appendix G

Drug Substance Olaparib

Study Code D0819C00003

Edition Number [REDACTED]

[REDACTED]

[REDACTED]

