5. STUDY CONDUCT

5.1 Restrictions during the study

5.1.1 Contraception

Female patients of child bearing potential and their partners, who are sexually active, must agree to the use of two highly effective forms of contraception in combination throughout the period of taking study treatment and for at least 1 month after last dose of study drug.

Male patients and their partners, who are sexually active and of childbearing potential, must agree to the use of two highly effective forms of contraception in combination, throughout the period of taking study treatment and for 3 months after last dose of study drug(s) due to the unknown effects of the study drug on the sperm. Male patients should not donate sperm throughout the period of taking study treatment and for 3 months following the last dose of study drug(s).

For details please refer to Appendix F Acceptable Birth Control Method.

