5.1.2 Olaparib and CYP3A

Patients should avoid concomitant use of drugs, herbal supplements and/or ingestion of foods known to modulate CYP3A enzyme activity (see Section 5.6.1) from the time they enter the screening period until 30 days after the last dose of study medication.

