5.6.1 CYP3A restrictions for olaparib arm

The use of any natural/herbal products or other "folk remedies" should be discouraged but use of these products, as well as use of all vitamins, nutritional supplements and all other concomitant medications must be recorded.

Olaparib produced little/no direct inhibition in vitro of CYPs 1A2, 2A6, 2B6, 2C8, 2C9, 2C19, 2D6 or 2E1 but inhibition of CYP3A4 was seen when olaparib was tested at high concentrations, suggesting that olaparib has the potential to cause clinically relevant interactions with other CYP3A substrates in the liver or gastrointestinal tract. Induction of CYP1A2, 2B6 and 3A4 has been shown in vitro, with CYP3A4 being most likely to be induced to a clinically relevant extent. Since olaparib may reduce exposure to substrates of CYP3A through enzyme induction, the efficacy of hormonal contraceptives may be reduced if co-administered with olaparib. In vitro data have also shown that the principal enzyme responsible for the formation of the 3 main metabolites of olaparib is CYP3A4/5 and in vivo data have shown that co-administration with itraconazole (a known CYP3A inhibitor) increases olaparib AUC by an average of 2.7-fold. Consequently, to ensure patient safety, the following potent inhibitors of CYP3A must not be used during this study for any patient receiving olaparib.

While this is not an exhaustive list, it covers the known potent inhibitors, which have most often previously been reported to be associated with clinically significant drug interactions:

- ketoconazole, itraconazole, ritonavir, indinavir, saquinavir, telithromycin, clarithromycin and nelfinavir

For patients taking any of the above, the required wash-out periods prior to starting study treatment is one week.

In addition, in vivo data have shown that co-administration with rifampicin (a known CYP inducer) reduces olaparib AUC by an average of 87%. Therefore, to avoid potential reductions in exposure due to drug interactions, the following CYP3A inducers should be avoided:

- Phenytoin, rifampicin, rifapentin, rifabutin, carbamazepine, phenobarbitone, nevirapine, modafinil and St John's Wort (*Hypericum perforatum*)

For patients taking any of the above, the required wash-out periods prior to starting study treatment are phenobarbitone 5 weeks, and for any of the others, 3 weeks.

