5.6.2 Effect of olaparib on other drugs

Olaparib can inhibit CYP3A4 and UGT1A1 in vitro. These findings suggest that olaparib has the potential to cause clinically significant interactions with other CYP3A4 and UGT1A1 substrates in the liver or GI tract. Therefore, caution should be exercised when substrates of CYP3A4 are combined with olaparib, in particular those with a narrow therapeutic margin (eg, simvastatin, cisapride, cyclosporine, ergot alkaloids, fentanyl, pimozide, sirolimus, tacrolimus and quetiapine). Substrates of UGT1A1 should also be given with caution in combination with olaparib (eg, irinotecan, nintedanib, ezetimibe, raltegravir or buprenorphine).

Induction of CYP1A2, 2B6 and 3A4 has been shown in vitro with CYP3A4 being most likely to be induced to a clinically relevant extent. The potential for olaparib to induce CYP2C9, CYP2C19 and Pgp is unknown. It cannot be excluded that olaparib upon co-administration may reduce the exposure to substrates of these metabolic enzymes and transport protein. The efficacy of hormonal contraceptives may be reduced if co-administered with olaparib.

In vitro, olaparib has been shown to be an inhibitor of Pgp, OATP1B1, OCT1, OCT2, OAT3, MATE1 and MATE2K and is a weak inhibitor of BRCP. It cannot be excluded that olaparib may increase the exposure to substrates of Pgp (eg, statins, digoxin, dabigatran, colchicine), OATP1B1 (eg, bosentan, glibenclamide, repaglinide, statins and valsartan), OCT1 (eg, metformin), OCT2 (eg, serum creatinine), OAT3, MATE1 and MATE2K. In particular, caution should be exercised if olaparib is administered in combination with any statin.

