4. EFFECT OF OLAPARIB ON OTHER DRUGS

Olaparib can inhibit CYP3A4 and UGT1A1 in vitro. These findings suggest that olaparib has the potential to cause clinically significant interactions with other CYP3A4 and UGT1A1 substrates in the liver or GI tract. Therefore, caution should be exercised when substrates of CYP3A4 are combined with olaparib, in particular those with a narrow therapeutic margin (eg, simvastatin, cisapride, cyclosporine, ergot alkaloids, fentanyl, pimozone, sirolimus, tacrolimus and quetiapine). Substrates of UGT1A1 should also be given with caution in combination with olaparib (eg, irinotecan, nintedanib, ezetimibe, raltegravir or buprenorphine).

Induction of CYP1A2, 2B6 and 3A4 has been shown in vitro with CYP3A4 being most likely to be induced to a clinically relevant extent. The potential for olaparib to induce CYP2C9, CYP2C19 and Pgp is unknown. It cannot be excluded that olaparib upon co-administration may reduce the exposure to substrates of these metabolic enzymes and transport protein. The efficacy of hormonal contraceptives may be reduced if co-administered with olaparib.

In vitro, olaparib has been shown to be an inhibitor of Pgp, OATP1B1, OCT1, OCT2, OAT3, MATE1 and MATE2K and is a weak inhibitor of BRCP. It cannot be excluded that olaparib may increase the exposure to substrates of Pgp (eg, statins, digoxin, dabigatran, colchicine), OATP1B1 (eg, bosentan, glibenclamide, repaglinide, statins and valsartan), OCT1 (eg, metformin), OCT2 (eg, serum creatinine), OAT3, MATE1 and MATE2K. In particular, caution should be exercised if olaparib is administered in combination with any statin.

Interaction of olaparib and specific co-medications

Preliminary data suggest that there is no clinically meaningful drug-drug interaction between anti-hormonal agents, tamoxifen (20 mg), anastrozole (1 mg) or letrozole (2.5 mg) when given in combination with olaparib (300 mg tablet), at steady state.

Clinical Study Protocol Appendix J

Drug Substance Olaparib

Study Code D0819C00003

Edition Number █

█

█

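### Appendix F accepts hormonal-plus-condom pairings as two highly effective methods without carrying over the protocol's own warning that olaparib may weaken hormonal contraception

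*Protocol*

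**What the plan says.** Protocol Section 5.1.1 says that sexually active women of childbearing potential and their partners "must agree to the use of two highly effective forms of contraception in combination" during treatment and for at least a month after the last dose. Its only pointer is "For details please refer to Appendix F Acceptable Birth Control Method".

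Appendix F opens with "Olaparib is regarded as a compound with medium/high foetal risk", repeats the two-method standard and presents its list as the way to meet it. Total abstinence is the stated alternative. Under hormonal methods it gives seven entries, beginning with "Normal and low dose combined oral pills PLUS male condom". All seven add a male condom, and none carries a qualification or a distinction by treatment arm.

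Elsewhere, Section 5.6.1 says that "the efficacy of hormonal contraceptives may be reduced if co-administered with olaparib", because olaparib may lower exposure to CYP3A substrates through enzyme induction. Section 5.6.2 and Appendix I, section 4, give the same warning.

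**The concern.** A site that follows 5.1.1 and Appendix F to the letter can approve, for a woman on olaparib, a pair whose hormonal half the protocol itself doubts. If that half is weakened, the pair may no longer be two highly effective forms, which is the standard the protocol sets.

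What is at stake is foetal exposure. Women of childbearing potential are eligible (inclusion criterion 12). Section 1.1.5 reports harm to embryofetal survival and development at doses without significant maternal toxicity. The schedule in Table 1 places pregnancy tests at screening and Day 1, and later tests depend on suspicion. Such testing detects a pregnancy but does not prevent one, so the choice of contraceptive is the main preventive safeguard.

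**Working it through.** No power, alpha or sample-size figure bears on this point. The check is a comparison of texts.

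1. **What the list accepts.** The hormonal entries in Appendix F, by route, are two oral (combined pill, desogestrel pill) and one each of injection, implant, transdermal system, intrauterine system and intravaginal device: 2 + 1 + 1 + 1 + 1 + 1 = 7. All are paired with a male condom. The non-hormonal entries are abstinence and three condom pairings (vasectomised partner, tubal occlusion, copper-banded IUD).

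2. **Where the warning stands.** It appears in three places: 5.6.1, 5.6.2 ("efficacy of hormonal contraceptives may be reduced if co-administered with olaparib") and Appendix I, section 4 ("The efficacy of hormonal contraceptives may be reduced if co-administered with olaparib"). It appears in neither 5.1.1 nor Appendix F.

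3. **What the warning rests on.** All three places cite in vitro induction and name CYP3A4 as the enzyme most likely to be induced to a degree that matters clinically. In vitro inhibition of CYP3A4 is also reported. No clinical contraceptive data are given, so the size of any loss of efficacy, and any difference between routes, is unknown.

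4. **Whether another passage closes the gap.**
   - Section 5.1.2, directly after the contraception text, does point to 5.6.1, but for items "known to modulate CYP3A enzyme activity (see Section 5.6.1", which the patient should avoid. That concerns what other agents do to olaparib, not what olaparib does to a contraceptive.
   - Section 5.6.2 asks for caution when CYP3A4 substrates are combined with olaparib. It does not say whether a hormonal method still counts towards the two.
   - Section 13.3.1 foresees study treatment interfering with a contraceptive, but only to decide whether a pregnancy is an adverse event.

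5. **Result.** Read together, the sections require two highly effective methods, count a hormonal method as one of them, and say that olaparib may reduce its efficacy. No passage tells the site how to reconcile these.

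**The case against.** The strongest reply is that the texts can stand together. The warning says efficacy may be reduced; it does not prohibit hormonal contraceptives, which are not among the agents 5.6.1 bars or says to avoid. Appendix F never accepts a hormonal method alone. Warning of a possible reduction while always requiring a barrier is coherent, and the protocol sets no numerical threshold for highly effective. Two of the three warnings are in the main body, in sections that sites consult for concomitant medication. The list also serves the chemotherapy arm and partners of male patients, for whom the olaparib interaction does not arise.

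Most of this stands, and it limits the weight of the point. It does not remove it. The condom provides a fallback, but the stated standard is two highly effective methods, not one plus another in doubt. A reader who goes where 5.1.1 points will not meet the warning.

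A reader might infer that women or sites were never warned. The documents do not support that: the warning is in the protocol, investigators are told to know the Investigator's Brochure, and the consent pages are not available. A reader might also take the seven hormonal entries, or the size of the olaparib arm, as a measure of risk. Neither is one. Entries on a list are not patients, and the arm includes women who are postmenopausal or sterilised and may include men.

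**Conclusion.** The inconsistency holds as a limited patient-safety gap. Section 5.1.1 and Appendix F accept seven hormonal-plus-condom pairings as two highly effective forms for all women of childbearing potential, while three other places in the same protocol warn that olaparib may weaken the hormonal component. The text comparison is certain. The clinical consequence is not: it depends on in vitro induction carrying over to patients, and neither its size nor the number of women concerned can be derived.

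It would be tempting to conclude that the hormonal pairings are inadequate on olaparib, or that a third method, sponsor safety-physician sign-off by route or a contraceptive agreement at screening is needed. The documents do not go that far. They give a possible reduction, no clinical estimate, and a condom in every pairing. The point supports a wording correction, graded as a cheap improvement.

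**What to change.** Add to Section 5.1.1 and to Appendix F: *Olaparib may reduce the efficacy of hormonal contraceptives (see 5.6.1, 5.6.2 and Appendix I). For women of childbearing potential assigned olaparib, a listed non-hormonal pairing or total abstinence is preferred; if a hormonal method is used, the male condom must not be omitted.*

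Leave the list unchanged for the chemotherapy arm and for partners of male patients.

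The cost is a sentence in two places and a notice to sites. Some women face a narrower preferred choice, since the non-hormonal pairings need a copper-banded IUD, tubal occlusion or a vasectomised partner. Because the wording states a preference and not a ban, the hormonal pairings remain available to them. Sample size, endpoints and analysis are unaffected.

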Appendix G

Guidelines for Evaluation of Objective Tumour Response Using RECIST

1. INTRODUCTION

This appendix details the implementation of RECIST 1.1 Guidelines ([Eisenhauer et al 2009](#)) for the D0819C00003 study with regards to Investigator assessment of tumour burden including protocol-specific requirements for this study.

2. DEFINITION OF MEASURABLE, NON-MEASURABLE, TARGET AND NON-TARGET LESIONS

Patients with at least one lesion (measurable and/or non-measurable) that can be accurately assessed at baseline by CT/MRI and is suitable for repeated assessment may be entered on this study.

Measurable:

A lesion, not previously irradiated, that can be accurately measured at baseline as ≥ 10 mm in the longest diameter (except lymph nodes which must have short axis ≥ 15 mm) with computed tomography (CT) or magnetic resonance imaging (MRI) and which is suitable for accurate repeated measurements.

Non-measurable:

- All other lesions, including small lesions (longest diameter <10 mm or pathological lymph nodes with ≥ 10 to <15 mm short axis at baseline*).
- Truly non-measurable lesions include the following: bone lesions, leptomeningeal disease, ascites, pleural / pericardial effusion, inflammatory breast disease, lymphangitic involvement of skin or lung, abdominal masses/abdominal organomegaly identified by physical examination that is not measurable by CT or MRI.
- Previously irradiated lesions**
- Skin lesions assessed by clinical examination
- Brain metastasis

* Nodes with <10 mm short axis are considered non-pathological and should not be recorded or followed as NTL.

**Localised post-radiation changes which affect lesion sizes may occur. Therefore, lesions that have been previously irradiated will not be considered measurable and must be selected as Non-Target Lesions (NTL) at baseline and followed up as part of the NTL assessment.

Special Cases:

- Lytic bone lesions or mixed lytic–blastic lesions, with identifiable soft tissue components, can be considered measurable if the soft tissue component meets the definition of measurability. Blastic lesions are considered non-measurable.
- Cystic metastases can be considered measurable lesions if they meet the criteria for measurability from a radiological point of view, but if non-cystic lesions are present in the same patient, these should be selected as target lesions.

Target lesions:

A maximum of 5 measurable lesions (with a maximum of 2 lesions per organ), representative of all lesions involved suitable for accurate repeated measurement, should be identified as target lesions (TL) at baseline.

Non-Target lesions:

All other lesions (or sites of disease) not recorded as TL should be identified as NTL at baseline.

